Appendix 5Response Evaluation Criteria in Solid Tumors, Version 1.1 (RECIST v1.1)

evaluations. In addition, if a lymph node lesion shrinks to a non-malignant size (short axis < 10 mm), this should be captured on the CRF as part of the assessment of non-target lesions.

RESPONSE CRITERIA

CRITERIA FOR TARGET LESIONS

Definitions of the criteria used to determine objective tumor response for target lesions are provided below:

- Complete response (CR): Disappearance of all target lesions
- Any pathological lymph nodes must have reduction in short axis to < 10 mm.
- Partial response (PR): At least a 30% decrease in the sum of diameters of all target lesions, taking as reference the baseline sum of diameters, in the absence of CR
- Progressive disease (PD): At least a 20% increase in the sum of diameters of target lesions, taking as reference the smallest sum of diameters on study (including baseline)
- In addition to the relative increase of 20%, the sum of diameters must also demonstrate an absolute increase of ≥ 5 mm.
- Stable disease (SD): Neither sufficient shrinkage to qualify for CR or PR nor sufficient increase to qualify for PD

CRITERIA FOR NON-TARGET LESIONS

Definitions of the criteria used to determine the tumor response for the group of non-target lesions are provided below. While some non-target lesions may actually be measurable, they need not be measured and instead should be assessed only qualitatively at the timepoints specified in the schedule of activities.

- CR: Disappearance of all non-target lesions and (if applicable) normalization of tumor marker level
- All lymph nodes must be non-pathological in size (< 10 mm short axis).
- Non-CR/Non-PD: Persistence of one or more non-target lesions and/or (if applicable) maintenance of tumor marker level above the normal limits
- PD: Unequivocal progression of existing non-target lesions

SPECIAL NOTES ON ASSESSMENT OF PROGRESSION OF NON-TARGET LESIONS

Patients with Measurable and Non-Measurable Disease

For patients with both measurable and non-measurable disease to achieve unequivocal progression on the basis of the non-target lesions, there must be an overall level of substantial worsening in non-target lesions in a magnitude that, even in the presence of SD or PR in target lesions, the overall tumor burden has increased sufficiently to merit discontinuation of therapy. A modest increase in the size of one or more non-target

Appendix 5Response Evaluation Criteria in Solid Tumors, Version 1.1 (RECIST v1.1)

lesions is usually not sufficient to qualify for unequivocal progression status. The designation of overall progression solely on the basis of change in non-target lesions in the face of SD or PR in target lesions will therefore be extremely rare.

NEW LESIONS

The appearance of new malignant lesions denotes disease progression; therefore, some comments on detection of new lesions are important. There are no specific criteria for the identification of new radiographic lesions; however, the finding of a new lesion should be unequivocal, that is, not attributable to differences in scanning technique, change in imaging modality, or findings thought to represent something other than tumor (for example, some "new" bone lesions may be simply healing or flare of pre-existing lesions). This is particularly important when the patient's baseline lesions show PR or CR. For example, necrosis of a liver lesion may be reported on a CT scan report as a "new" cystic lesion, which it is not.

A lesion identified during the study in an anatomical location that was not scanned at baseline is considered a new lesion and will indicate disease progression.

If a new lesion is equivocal, for example because of its small size, continued therapy and follow-up evaluation will clarify if it represents truly new disease. If repeat scans confirm there is definitely a new lesion, progression should be declared using the date of the initial scan.

CRITERIA FOR OVERALL RESPONSE AT A SINGLE TIMEPOINT

Table 1 provides a summary of the overall response status calculation at each response assessment timepoint for patients who have measurable disease at baseline.

Appendix 5Response Evaluation Criteria in Solid Tumors, Version 1.1 (RECIST v1.1)

Table 1 Criteria for Overall Response at a Single Timepoint: Patients with Target Lesions (with or without Non-Target Lesions)

Target Lesions	Non-Target Lesions	New Lesions	Overall Response
CR	CR	No	CR
CR	Non-CR/non-PD	No	PR
CR	Not all evaluated	No	PR
PR	Non-PD or not all evaluated	No	PR
SD	Non-PD or not all evaluated	No	SD
Not all evaluated	Non-PD	No	NE
PD	Any	Yes or no	PD
Any	PD	Yes or no	PD
Any	Any	Yes	PD

CR=complete response; NE=not evaluable; PD=progressive disease; PR=partial response; SD=stable disease.

MISSING ASSESSMENTS AND NOT-EVALUABLE DESIGNATION

When no imaging/measurement is done at all at a particular timepoint, the patient is not evaluable at that timepoint. If measurements are made on only a subset of target lesions at a timepoint, usually the case is also considered not evaluable at that timepoint, unless a convincing argument can be made that the contribution of the individual missing lesions would not change the assigned timepoint response. This would be most likely to happen in the case of PD. For example, if a patient had a baseline sum of 50 mm with three measured lesions and during the study only two lesions were assessed, but those gave a sum of 80 mm, the patient will have achieved PD status, regardless of the contribution of the missing lesion.

SPECIAL NOTES ON RESPONSE ASSESSMENT

Patients with a global deterioration in health status requiring discontinuation of treatment without objective evidence of disease progression at that time should be reported as "symptomatic deterioration." Every effort should be made to document objective progression even after discontinuation of treatment. Symptomatic deterioration is not a descriptor of an objective response; it is a reason for stopping study therapy. The objective response status of such patients is to be determined by evaluation of target and non-target lesions as shown in [Table 1](#).

For equivocal findings of progression (e.g., very small and uncertain new lesions; cystic changes or necrosis in existing lesions), treatment may continue until the next scheduled

Appendix 5Response Evaluation Criteria in Solid Tumors, Version 1.1 (RECIST v1.1)

assessment. If at the next scheduled assessment, progression is confirmed, the date of progression should be the earlier date when progression was suspected.

REFERENCES

Appendix 6

Immune-Modified Response Evaluation Criteria in Solid Tumors (imRECIST)

Conventional response criteria may not be adequate to characterize the anti-tumor activity of immunotherapeutic agents, which can produce delayed responses that may be preceded by initial apparent radiographic progression, including the appearance of new lesions. Therefore, immune-modified response criteria have been developed to incorporate new lesions into the assessment of total tumor burden and allow radiographic progression to be confirmed at a subsequent assessment.

Immune-modified Response Evaluation Criteria in Solid Tumors (imRECIST), as described within this appendix, were adapted from RECIST, Version 1.1 (v1.1) (Eisenhauer et al. 2009), in the same manner that immune-related response criteria were adapted from WHO criteria (Wolchok et al. 2009) and RECIST v1.0 (Nishino et al. 2014). When not otherwise specified, RECIST v1.1 conventions will apply. Differences between imRECIST and RECIST v1.1 are summarized in [Table 1](#).

Table 1 Comparison of RECIST v1.1 and imRECIST

	RECIST v1.1	imRECIST
Measurable new lesions	Always represent progression	Incorporated into the total tumor burden ^a and followed
Non-measurable new lesions	Always represent progression	Do not represent progression, but preclude CR
Non-target lesions	Contribute to defining CR, PR, SD, and PD	Contribute to defining CR only
CR	Disappearance of all lesions	Disappearance of all lesions
PR	≥30% decrease in sum of diameters of target lesions, in the absence of CR, new lesions, and unequivocal progression in non-target lesions	≥30% decrease in tumor burden, ^a in the absence of CR
PD	≥20% increase in sum of diameters of target lesions, unequivocal progression in non-target lesions, and/or appearance of new lesions	≥20% increase in tumor burden ^a
SD	Neither sufficient shrinkage to qualify for CR or PR nor sufficient increase to qualify for PD	Neither sufficient shrinkage to qualify for CR or PR nor sufficient increase to qualify for PD

CR=complete response; PD=progressive disease; PR=partial response; RECIST=Response Evaluation Criteria in Solid Tumors; SD=stable disease.

^a Tumor burden is the sum of diameters of target lesions and measurable new lesions.

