Intracranial disease must be followed by MRI. Extracranial tumour assessments will include contrast-enhanced CT or MRI scans of the chest, abdomen and pelvis. Imaging of the neck should be included if clinically indicated. If a CT scan with contrast is contraindicated (e.g., in patients with impaired renal clearance), a non-contrast CT scan of the chest may be performed along with MRI scans of the abdomen, pelvis and head. In the event a positron emission tomography (PET)/CT scanner is used for tumour assessments, the CT portion of the PET/CT must meet criteria for diagnostic quality. Clinical disease assessments by physical examination should be performed for patients with palpable/superficial lesions. Tumour measurements for each patient should be made by the same investigator or radiologist, if feasible, ideally using the same assessment technique or procedure throughout the study. Results must be reviewed by the investigator before dosing at the next cycle.

Disease status will be determined according to RECIST v1.1 (see [Appendix 5](#)) with a modified measurability definition for intracranial lesions (≥ 0.5 cm by MRI) and allowing up to five intracranial target lesions (in addition to any extracranial target lesions). Exploratory analyses of disease status will include evaluations by immune-modified RECIST (see [Appendix 6](#)), RECIST v1.1 modified by excluding any SRT lesions from the sum of largest diameters from baseline onwards (if applicable), and iRANO criteria (see [Appendix 7](#)).

Disease responses for all endpoints will be confirmed by two consecutive assessments at least four weeks apart. Tumour assessments showing disease progression must be repeated approximately four weeks later regardless of whether treatment is continued

beyond progression. If disease progression is not confirmed, the subsequent tumour assessment should occur at least four weeks later. However, post-progression assessments may be conducted sooner for patients continuing study treatment beyond progression if necessary e.g., due to clinical progression. Objective response (CR or PR) must be confirmed by repeat assessments ≥ 4 weeks after initial documentation. In the case of SD, tumour measurements must meet criteria for SD ≥ 6 weeks after initiation of study treatment.

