- Partial response (PR): At least a 30% decrease in the sum of diameters of all target lesions plus measurable new lesions (up to a maximum of five total or two per organ), taking as reference the baseline sum of diameters, in the absence of CR
- Progressive disease (PD): At least a 20% increase in the sum of diameters of all target lesions plus measurable new lesions (up to a maximum of five total or two per

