Appendix 6:Immune-Modified Response Evaluation Criteria in Solid Tumors (imRECIST)

organ), taking as reference the smallest sum of diameters on study (including baseline)

In addition to the relative increase of 20%, the sum of diameters must also demonstrate an absolute increase of ≥ 5 mm.

New lesions alone do not qualify as progressive disease. However, their contribution to total tumor burden is factored into the sum of the diameters, which is used to determine the overall imRECIST tumor response.

- Stable disease (SD): Neither sufficient shrinkage to qualify for CR or PR nor sufficient increase to qualify for PD

CRITERIA FOR OVERALL RESPONSE AT A SINGLE TIMEPOINT

[Table 1](#) provides a summary of the overall response status calculation at each response assessment timepoint for patients who have measurable disease at baseline.

Table 1 Criteria for Overall Response at a Single Timepoint: Patients with Target Lesions (with or without Non-Target Lesions)

Target Lesions and Measurable New Lesions ^a	Non-Target Lesions and Non-Measurable New Lesions ^b	Overall Response
CR	Absent	CR
CR	Present or not all evaluated	PR
PR	Any	PR
SD	Any	SD
Not all evaluated	Any	NE
PD	Any	PD

CR=complete response; NE=not evaluable; PD=progressive disease; PR=partial response; SD=stable disease.

^a Up to a maximum of five measurable new lesions total (and a maximum of two lesions per organ) can be included in the calculation of tumor burden, in addition to the target lesions identified at baseline.

^b Also includes measurable new lesions in excess of five total or two per organ.

MISSING ASSESSMENTS AND NOT-EVALUABLE DESIGNATION

When no imaging/measurement is done at all at a particular timepoint, the patient is not evaluable at that timepoint. If measurements are made on only a subset of target or measurable new lesions at a timepoint, usually the case is also considered not evaluable at that timepoint, unless a convincing argument can be made that the contribution of the individual missing lesions would not change the assigned timepoint response. This would be most likely to happen in the case of PD. For example, if a patient had a baseline sum of 50 mm with three measured lesions and during the study only two lesions were assessed, but those gave a sum of 80 mm, the patient will have achieved PD status, regardless of the contribution of the missing lesion.

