#### **5.4.2.4 Intracranial, Extracranial and Overall Progression-Free Survival – RECIST**

Intracranial, extracranial, and overall progression-free survival (PFS) are defined as the time from study treatment initiation to the first occurrence of disease progression, as

determined by the investigator according to RECIST v1.1, or death from any cause, whichever occurs first. Data for patients who have not experienced disease progression or death at the time of analysis data cutoff will be censored at the last evaluable tumor assessment date.

Kaplan-Meier methodology will be used to estimate median intracranial, extracranial, and overall PFS. Kaplan-Meier curves will be provided. The 95% CI of the median PFS will be constructed using the Brookmeyer and Crowley method (Brookmeyer and Crowley 1982).

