### **5.5.1.3 Intracranial, Extracranial, and Overall Progression-Free Survival – Immune-Modified RECIST**

Intracranial, extracranial, and overall PFS are defined as described in Section [5.4.2.4](#) but determined by the investigator according to immune-modified RECIST.

Intracranial, extracranial, and overall PFS will be analyzed using the same methods as described in Section [5.4.2.4](#).

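### Exploratory imRECIST PFS and DOR end at the first PD, so a transient rise in target-lesion burden that reverses at the mandated repeat scan still counts as an event

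*Protocol*

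**What the plan says.** - **Purpose.** The opening of Protocol Appendix 6 gives two reasons for immune-modified criteria: to bring new lesions into the tumour burden, and to "allow radiographic progression to be confirmed at a subsequent assessment".
- **PD rule.** Under Response Criteria in Appendix 6, PD is "At least a 20% increase in the sum of diameters of all target lesions plus measurable new lesions", measured against the smallest sum on study, and "the sum of diameters must also demonstrate an absolute increase of ≥ 5 mm". The comparison table at the start of the appendix and the single-timepoint table at its end add no second assessment. New lesions alone are not PD, and non-target lesions contribute only to CR.
- **imRECIST PFS.** SAP 5.5.1.3 takes the definition in SAP 5.4.2.4, "but determined by the investigator according to immune-modified RECIST". SAP 5.4.2.4 defines PFS as the "time from study treatment initiation to the first occurrence of disease progression" or death.
- **imRECIST DOR.** SAP 5.5.1.4 takes SAP 5.4.2.5 in the same way; there, DOR runs from a confirmed response to progression or death. Protocol 6.4.3 likewise refers imRECIST response, PFS and DOR back to the methods of 6.4.2.
- **Repeat scan.** Protocol 4.5.6: "Tumour assessments showing disease progression must be repeated approximately four weeks later", whether or not treatment continues. It may be done sooner if needed in patients treated beyond progression.

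**The concern.** Of the two stated purposes, only the first is carried through to the analysis. New lesions are handled, but no rule lets the repeat scan overturn an apparent progression in imRECIST PFS or DOR. Protocol 3.3.5 describes response after an apparent increase in tumour burden and allows treatment to continue because of it. If that increase is growth of existing target lesions, the imRECIST endpoint records progression exactly as RECIST v1.1 would.

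At stake is what these exploratory estimates mean. Some patients could be imRECIST responders whose imRECIST PFS ended before their response began, and responders with a later transient rise would have their DOR cut short. If the rule is left to be settled once the data are seen, it could also be chosen in the light of the results.

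**Working it through.** The plan states no figure on this point, so there is none to reproduce. The check applies the written rules to one constructed patient and then sizes the effect.

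**1. Constructed patient.** The sums of diameters are assumed, with no new lesions and stable non-target disease. Scan times follow the protocol: week 8, a repeat about four weeks after PD, then the regular schedule.

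| Week | Sum (mm) | Change from baseline | Change from smallest earlier sum | Status |
|---|---|---|---|---|
| 0 | 50 | – | – | – |
| 8 | 62 | +24% | +24%, +12 mm | PD |
| 12 | 34 | −32% | −32% | PR |
| 16 | 32 | −36% | −6% | PR, confirmed |
| 24 | 30 | −40% | −6% | PR |
| 32 | 30 | −40% | 0% | PR |
| 40 | 40 | −20% | +33%, +10 mm | PD |

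- Week 8: 62/50 − 1 = 24% and 62 − 50 = 12 mm, so both thresholds are passed. imRECIST PFS ends at week 8. RECIST v1.1 uses the same 20% and 5 mm thresholds for target lesions, so its date is also week 8.
- Weeks 12 and 16: both scans are at least 30% below baseline and four weeks apart. Nothing in SAP 5.5.1.2 bars a response after PD, so the patient is an imRECIST responder from week 12, four weeks after the PFS event.
- If a PD reversed at the repeat scan were set aside, the next candidate event would be week 40 (40/30 − 1 = 33%, 10 mm), subject to its own repeat scan.
- DOR: the week 8 rise precedes the response, so it does not shorten DOR. The week 40 rise does: DOR ends at 40 − 12 = 28 weeks, even if the repeat scan falls back below 1.2 × 30 = 36 mm.

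**2. Does another rule rescue the endpoint?** Appendix 6 falls back on RECIST v1.1 where it is silent. The confirm-and-back-date text in Appendix 5 covers equivocal findings only, such as tiny uncertain new lesions, cystic change or necrosis. A clear rise of 20% and 5 mm is not among them. Appendix 7 (iRANO) has explicit confirmation and back-dating, but here iRANO supports only an ORR endpoint (SAP 5.5.1.1).

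**3. Number of patients.** The rate q of target-burden pseudoprogression is assumed at 2% to 10%. The expected number is n × q, and the chance of at least one is 1 − (1 − q)^n.

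| n | q | Expected | At least one |
|---|---|---|---|
| 50 evaluable | 2% | 1.0 | 63.6% |
| 50 evaluable | 5% | 2.5 | 92.3% |
| 50 evaluable | 10% | 5.0 | 99.5% |
| 60 treated | 2% | 1.2 | 70.2% |
| 60 treated | 10% | 6.0 | 99.8% |

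**4. Effect on the PFS curve.** Ignoring censoring, once the transient rises have occurred the curve is too low by q × S(t), where S(t) is the proportion of affected patients truly event-free at time t. Since S(t) ≤ 1, the shortfall cannot exceed q: 2 to 10 percentage points. As an illustration, suppose affected patients are event-free for 4 months and then have exponential PFS with median 8 months. Then S(6 months) = 2^(−2/8) = 0.841, and the six-month shortfall is 0.02 × 0.841 = 1.7 points to 0.10 × 0.841 = 8.4 points.

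**The case against.** The strongest reply is that this is missing detail, not a wrong rule. The response table in Appendix 6 is explicitly for one timepoint and could not hold a two-scan rule. Protocol 4.5.6 and 4.6.1 refer to confirmed progression, and the SAP leaves PD to the investigator under imRECIST, so first progression might be read as first confirmed progression.

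That reading is possible but not what is written. Where the plan wants confirmation it says so: every ORR definition names two consecutive assessments. The PFS and DOR definitions name no second assessment for progression, and the PD rule that they call on is met by one scan. A programmer following the text would use the first PD. First occurrence is explicit for PFS; for DOR it follows from the endpoint running to progression.

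Other parts of the reply stand, and rule out stronger inferences that a reader might draw:

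- Appendix 6 does not require confirmation. It says that the criteria were developed to allow it.
- The repeat scan is not unused. It governs treatment beyond progression, the timing of the next scan and how long assessments continue, and it can contribute to an imRECIST response. It is simply not tied to the imRECIST PFS or DOR event.
- No formal comparison of RECIST with imRECIST is planned, so no planned contrast is biased. The only concordance summary, in SAP 5.3.3, is investigator against IRC.
- imRECIST does remove some pseudoprogression: PD from new lesions alone and from non-target growth.
- A rule dropping every PD followed by a non-PD scan would be unsafe. Patients whose progression is limited to at most three intracranial lesions may receive SRT and stay on treatment. If SRT shrank those lesions before the repeat scan, a true progression would be erased.

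**Conclusion.** The point holds for imRECIST PFS and DOR, and only there. As written, a reversed rise in target-lesion burden (with or without measurable new lesions contributing to the sum) is an event, which leaves the second stated purpose of the criteria unimplemented.

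The likely scale is 1 to 5 of 50 evaluable patients, with a bound on the PFS shortfall of 2 to 10 percentage points. Both rest on an assumed rate that the documents do not supply. The 1.7 to 8.4 point illustration also assumes unusually durable control in the affected patients. In Cohort 2, atezolizumab starts in Cycle 2 and the first scan is in the last week of that cycle, so immune-related swelling has had only about four weeks to appear by then.

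A reader might infer that the trial's main result is in doubt. It is not: IRC intracranial ORR, the sample size and the RECIST v1.1 endpoints do not use this rule. These endpoints are exploratory, and all analyses are descriptive. The reason to act is that the change is cheap, the scans are already required, and the rule is better fixed before the results are known.

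**What to change.** In SAP 5.5.1.3 and 5.5.1.4, with one matching line in Protocol Appendix 6, state that:

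- imRECIST PD is an event, dated to the first PD scan, if the protocol-required repeat assessment is also PD. Use the protocol's own timing (about four weeks, sooner where allowed), not a strict four-week minimum.
- PD with no later evaluable scan is an event at its first date.
- PD reversed at the repeat scan is not an event, unless the progressing lesions received SRT, or another new anti-cancer treatment was given, before that scan. In that case the first PD date stands.

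This changes only the analysis rule, not treatment or the scan schedule. The cost is a few lines of text, a little extra programming that must also read SRT and subsequent-treatment dates, and reliance on a stated default for patients without a repeat scan.
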